7.1.9 Interim Analysis

Not applicable

8 ADVERSE EVENTS

8.1 Definitions

8.1.1 Adverse Drug Reaction (ADR)

An adverse reaction (ADR) is a response to a medicinal product which is noxious and unintended. Response in this context means that a causal relationship between a medicinal product and an adverse event is at least a reasonable possibility. This includes adverse reactions which arise from: use of a medicinal product within the terms of the marketing authorization; use outside the terms of the marketing authorization, including overdose, misuse, abuse and medication errors; and occupational exposure*.

* This corresponds to the exposure to a medicinal product for human use as a result of one's occupation, such as nurses who may handle products routinely in their occupational setting.

8.1.2 Adverse Event Definition

Adverse event (AE) means any untoward medical occurrence in a patient or subject administered a pharmaceutical product; the untoward medical occurrence does not necessarily have a causal relationship with this treatment. An AE can therefore be any unfavorable and unintended sign (including an abnormal laboratory finding), symptom, or disease temporally associated with the use of a medicinal (investigational) product whether or not it is related to the medicinal product. This includes any newly occurring event, or a previous condition that has increased in severity or frequency since the administration of study drug.

An abnormal laboratory value will not be assessed as an AE unless that value leads to discontinuation or delay in treatment, dose modification, therapeutic intervention, or is considered by the investigator to be a clinically significant change from baseline.

8.1.3 Serious Adverse Event Definition

Serious adverse event (SAE) means any untoward medical occurrence that at any dose:

- Results in **death**.
- Is **life-threatening** (refers to an AE in which the patient was at risk of death at the time of the event. It does not refer to an event which hypothetically might have caused death if it were more severe).
- Requires inpatient **hospitalization or prolongation of an existing hospitalization** (see clarification in the paragraph below on planned hospitalizations).
- Results in **persistent or significant disability or incapacity**. (Disability is defined as a substantial disruption of a person's ability to conduct normal life functions).
- Is a **congenital anomaly/birth defect**.
- Is a **medically important event**. This refers to an AE that may not result in death, be immediately life threatening, or require hospitalization, but may be considered serious

when, based on appropriate medical judgment, may jeopardize the patient, require medical or surgical intervention to prevent one of the outcomes listed above, or involves suspected transmission via a medicinal product of an infectious agent. Examples of such medical events include allergic bronchospasm requiring intensive treatment in an emergency room or at home, blood dyscrasias or convulsions that do not result in inpatient hospitalization, or the development of drug dependency or drug abuse; any organism, virus, or infectious particle (e.g., prion protein transmitting Transmissible Spongiform Encephalopathy), whether pathogenic or non-pathogenic, is considered an infectious agent.

Clarification should be made between a serious AE (SAE) and an AE that is considered severe in intensity (Grade 3 or 4), because the terms serious and severe are NOT synonymous. The general term severe is often used to describe the intensity (severity) of a specific event; the event itself, however, may be of relatively minor medical significance (such as a Grade 3 headache). This is NOT the same as serious, which is based on patient/event outcome or action criteria described above, and is usually associated with events that pose a threat to a patient's life or ability to function. A severe AE (Grade 3 or 4) does not necessarily need to be considered serious. For example, a white blood cell count of 1000/mm³ to less than 2000 is considered Grade 3 (severe) but may not be considered serious. Seriousness (not intensity) serves as a guide for defining regulatory reporting obligations.

8.2 Procedures for Reporting Serious Adverse Events

AEs may be spontaneously reported by the patient and/or in response to an open question from study personnel or revealed by observation, physical examination, or other diagnostic procedures. Any clinically relevant deterioration in laboratory assessments or other clinical finding is considered an AE. When possible, signs and symptoms indicating a common underlying pathology should be noted as one comprehensive event. AEs which are serious must be reported to Millennium/Takeda Pharmacovigilance (or designee) from the first dose of brentuximab vedotin up to and including 30 days after administration of the last dose of brentuximab vedotin. Any SAE that occurs at any time after completion of brentuximab vedotin treatment or after the designated follow-up period that the sponsor-investigator and/or sub-investigator considers to be related to any study drug must be reported to Millennium/Takeda Pharmacovigilance (or designee). Planned hospital admissions or surgical procedures for an illness or disease that existed before the patient was enrolled in the trial are not to be considered AEs unless the condition deteriorated in an unexpected manner during the trial (e.g., surgery was performed earlier or later than planned). All SAEs should be monitored until they are resolved or are clearly determined to be due to a patient's stable or chronic condition or intercurrent illness(es).

Since this is an investigator-initiated study, the principal investigator, [name], also referred to as the sponsor-investigator, is responsible for reporting serious adverse events (SAEs) to any regulatory agency and to the sponsor- investigator's EC or IRB. Regardless of expectedness or causality, all SAEs must also be reported to Millennium/Takeda Pharmacovigilance (or designee) within 24 hours of the sponsor-investigator's observation or awareness of the event (contact information provided below).

The sponsor-investigator should fax the SAE Form within 24 hours after becoming aware of the event. A sample of an SAE Form will be provided. Follow-up information on the SAE may be requested by Millennium/Takeda. The SAE report must include event term(s), serious criteria, and the sponsor-investigator's or sub-investigator's determination of both the intensity of the event(s) and the causality of the event(s) in relationship to study drug administration. Intensity for each SAE, including any lab abnormalities, will be determined by using the NCI CTCAE version used at your institution, as a guideline, whenever possible. The criteria are available online at <http://ctep.cancer.gov/reporting/ctc.html>.

In the event that this is a multisite study, the sponsor-investigator is responsible to ensure that the SAE reports are sent to Millennium/Takeda Pharmacovigilance (or designee) from all sites participating in the study. Sub-investigators must report all SAEs to the sponsor-investigator so that the sponsor-investigator can meet his/her foregoing reporting obligations to the required regulatory agencies and to Millennium/Takeda Pharmacovigilance, unless otherwise agreed between the sponsor-investigator and sub-investigator(s).

Relationship to all study drugs for each SAE will be determined by the sponsor-investigator or sub-investigator by responding yes or no to the question: Is there a reasonable possibility that the AE is associated with the study drug(s)?

Sponsor-investigator must also provide Millennium/Takeda Pharmacovigilance with a copy of all communications with applicable regulatory authorities related to the study or study drug(s), as soon as possible but no later than 4 calendar days of such communication.

Millennium/Takeda Pharmacovigilance

**SAE and Pregnancy Reporting Contact Information
US and Canada**

Toll-Free [contact]

E-mail: [contact]

All other countries (Rest of World)

[contact]

E-mail: [contact]

8.3 Procedures for Reporting Drug Exposure During Pregnancy and Birth Events

If a woman becomes pregnant or suspects that she is pregnant while participating in this study, she must inform the investigator immediately and permanently discontinue study drug. All pregnancies and suspected pregnancies must be reported to Millennium/Takeda Pharmacovigilance (or designee) immediately (see Section 8.2 for contact information). The pregnancy must be followed for the final pregnancy outcome (i.e., delivery, still birth, miscarriage) and Millennium/Takeda Pharmacovigilance will request this information from the sponsor-investigator.

If a female partner of a male patient becomes pregnant during the male patient's participation in this study, this must be reported to Millennium/Takeda Pharmacovigilance or designee

immediately (see Section 8.2 for contact information). Every effort should be made to follow the pregnancy for the final pregnancy outcome.

9 ADMINISTRATIVE REQUIREMENTS

9.1 Good Clinical Practice

The study will be conducted in accordance with the International Conference on Harmonisation (ICH) for Good Clinical Practice (GCP) and the appropriate regulatory requirement(s). The investigator will be thoroughly familiar with the appropriate use of the study drug as described in the protocol and Investigator's Brochure. Essential clinical documents will be maintained to demonstrate the validity of the study and the integrity of the data collected. Master files should be established at the beginning of the study, maintained for the duration of the study and retained according to the appropriate regulations.

9.2 Ethical Considerations

The study will be conducted in accordance with applicable regulatory requirement(s) and will adhere to GCP standards. The IRB/IEC will review all appropriate study documentation in order to safeguard the rights, safety and well-being of the patients. The study will be conducted only at sites where IRB/IEC approval has been obtained. The protocol, Investigator's Brochure, informed consent form, advertisements (if applicable), written information given to the patients (including diary cards), safety updates, annual progress reports, and any revisions to these documents will be provided to the IRB/IEC by the investigator. Millennium requests that informed consent documents be reviewed by Millennium or designee prior to IRB/IEC submission.

9.3 Patient Information and Informed Consent

After the study has been fully explained, written informed consent will be obtained from either the patient or his/her guardian or legal representative before study participation. The method of obtaining and documenting the informed consent and the contents of the consent must comply with the ICH-GCP and all applicable regulatory requirement(s).

9.4 Patient Confidentiality

In order to maintain patient privacy, all data capture records, drug accountability records, study reports and communications will identify the patient by initials and the assigned patient number. If requested, the investigator will grant monitor(s) and auditor(s) from Millennium or its designees and regulatory authority(ies) access to the patient's original medical records for verification of data gathered on the data capture records and to audit the data collection process. The patient's confidentiality will be maintained and will not be made publicly available to the extent permitted by the applicable laws and regulations.

9.5 Investigator Compliance

The investigator will conduct the study in compliance with the protocol given approval/favorable opinion by the IRB/IEC and the appropriate regulatory authority(ies). Changes to the protocol will require approval from Millennium and written IRB/IEC approval/favorable opinion prior to implementation, except when the modification is needed to eliminate an immediate hazard(s) to patients. The IRB/IEC may provide, if applicable regulatory authority(ies) permit, expedited review and approval/favorable opinion for minor change(s) in ongoing studies that have the

approval /favorable opinion of the IRB/IEC. The investigator will submit all protocol modifications to Millennium and the regulatory authority(ies) in accordance with the governing regulations.

Any departures from the protocol must be fully documented in the source documents.

9.6 On-site Audits

Regulatory authorities, the IEC/IRB and/or Millennium may request access to all source documents, data capture records, and other study documentation for on-site audit or inspection. Direct access to these documents must be guaranteed by the investigator, who must provide support at all times for these activities.

9.7 Investigator and site Responsibility for Drug Accountability

Accountability for the study drug at all study sites is the responsibility of the principal investigator. The investigator will ensure that the drug is used only in accordance with this protocol. Drug accountability records indicating the drug's delivery date to the site, inventory at the site, use by each patient, and amount returned to Millennium or a designee or disposal of the drug (if applicable and if approved by Millennium) will be maintained by the clinical site. Accountability records will include dates, quantities, lot numbers, expiration dates (if applicable), and patient numbers.

9.8 Product Complaints

A product complaint is a verbal, written, or electronic expression that implies dissatisfaction regarding the identity, strength, purity, quality, or stability of a drug product. Individuals who identify a potential product complaint situation should immediately contact MedComm Solutions (see below) and report the event. Whenever possible, the associated product should be maintained in accordance with the label instructions pending further guidance from a Millennium/Takeda Quality representative.

A medication error is a preventable event that involves an identifiable patient and that leads to inappropriate medication use, which may result in patient harm. While overdoses and underdoses constitute medication errors, doses missed inadvertently by a patient do not. Individuals who identify a potential medication error situation should immediately contact MedComm Solutions (see below) and report the event.

For Product Complaints or Medication Errors,
call MedComm Solutions at

(US and International)
[contact]

Product complaints and medication errors in and of themselves are not AEs. If a product complaint or medication error results in an SAE, an SAE form should be completed and sent to Millennium/Takeda (refer to Section 8.2).

9.9 Closure of the Study

This study may be prematurely terminated, if in the opinion of the investigator or Millennium/Takeda, there is sufficient reasonable cause. Written notification documenting the reason for study termination will be provided to the investigator or Millennium/Takeda by the terminating party.

Circumstances that may warrant termination include, but are not limited to:

- Determination of unexpected, significant, or unacceptable risk to patients
- Failure to enter patients at an acceptable rate
- Insufficient adherence to protocol requirements
- Insufficient, incomplete and/or unevaluable data
- Determination of efficacy based on interim analysis
- Plans to modify, suspend or discontinue the development of the drug

Should the study be closed prematurely, all study materials must be returned to Millennium/Takeda.

9.10 Record Retention

The investigator will maintain all study records according to ICH-GCP and applicable regulatory requirement(s).

10 USE OF INFORMATION

All information regarding brentuximab vedotin supplied by Millennium/Takeda to the investigator is privileged and confidential information. The investigator agrees to use this information to accomplish the study and will not use it for other purposes without consent from Millennium/Takeda. It is understood that there is an obligation to provide Millennium/Takeda with complete data obtained during the study. The information obtained from the clinical study will be used toward the development of brentuximab vedotin and may be disclosed to regulatory authority(ies), other investigators, corporate partners, or consultants as required.

Upon completion of the clinical study and evaluation of results by Millennium/Takeda, the hospital or institution and/or investigator may publish or disclose the clinical trial results pursuant to the terms contained in the applicable Clinical Trial Agreement.

12 APPENDICES

12.1 Common Terminology Criteria for Adverse Events Version 4.03⁽⁴⁾

<http://ctep.cancer.gov/reporting/ctc.html>

12.2 New York Heart Association Classification of Cardiac Disease⁽⁵⁾

Class	Functional Capacity	Objective Assessment
I	Patients with cardiac disease but without resulting limitations of physical activity. Ordinary physical activity does not cause undue fatigue, palpitation, dyspnea, or 54angina pain.	No objective evidence of cardiovascular disease.
II	Patients with cardiac disease resulting in slight limitation of physical activity. They are comfortable at rest. Ordinary physical activity results in fatigue, palpitation, dyspnea, or 54angina pain.	Objective evidence of minimal cardiovascular disease.
III	Patients with cardiac disease resulting in marked limitation of physical activity. They are comfortable at rest. Less than ordinary activity causes fatigue, palpitation, dyspnea, or angina pain.	Objective evidence of moderately severe cardiovascular disease.
IV	Patients with cardiac disease resulting in inability to carry on any physical activity without discomfort. Symptoms of heart failure or the 54angina syndrome may be present even at rest. If any physical activity is undertaken, discomfort is increased.	Objective evidence of severe cardiovascular disease.

Source: The Criteria Committee of New York Heart Association. Nomenclature and Criteria for Diagnosis of Diseases of the Heart and Great Vessels. 9th Ed. Boston, MA: Little, Brown & Co; 1994:253-256.

12.3 Revised response criteria for malignant lymphoma

Complete Remission (CR)

1. Complete disappearance of all detectable clinical evidence of disease and disease-related symptom if present prior to therapy.
2. The spleen and/or liver, if considered enlarged prior to therapy on the basis of a physical examination or CT scan, should not be palpable on physical examination and should be considered normal size by imaging studies, and nodules related to lymphoma should disappear.
3. If the bone marrow was involved by lymphoma prior to treatment, the infiltrate must have been cleared on repeat bone marrow biopsy and EBV should be negative by EBV in situ hybridization (ISH).
4. In patients for whom FDG by PET is avid, incorporation of interim PET imaging results as follows: All CR requirements as described above. However, if a patient's PET scan was positive before therapy, a post-treatment residual mass of any size is permitted as long as it is PET negative

Partial Remission (PR)

1. $\geq 50\%$ decrease in sum of the product of the diameters (SPD) of up to 6 of the largest dominant nodes or nodal masses.
2. No increase in the size of the other nodes, liver, or spleen.
3. Splenic and hepatic nodules must regress by $\geq 50\%$ in their SPD or, for single nodules, in the greatest transverse diameter.
4. With the exception of splenic and hepatic nodules, involvement of other organs is usually assessable and no measurable disease should be present.
5. Bone marrow assessment is irrelevant for determination of a PR if the sample was positive prior to treatment. However, if positive, the EBV-positivity should be specified by EBV ISH. Patients who achieve a CR by the above criteria, but who have persistent morphologic or molecular bone marrow involvement will be considered partial responders.
6. No new sites of disease should be observed (e.g., nodes > 1.5 cm in any axis).
7. For patients with FDG-avidity, an interim assessment should be made. For patients whose PET scan was positive before therapy, the post-treatment PET scan should be positive in at

least one previously involved site.

Stable Disease (SD)

1. Failure to attain the criteria needed for a CR or PR, but not fulfilling those for progressive disease
2. PET imaging should be positive at prior sites of disease with no new areas of involvement on the post-treatment PET scan.

Relapsed Disease (RD; after CR) or Progressive Disease (PD; for Patients with PR or SD)

1. Appearance of any new lesion more than 1.5 cm in any axis during or at the end of therapy, even if other lesions are decreasing in size.
2. At least a 50% increase from nadir in the SPD of any previously involved nodes, or in a single involved node, or the size of other lesions (e.g., splenic or hepatic nodules). To be considered progressive disease, a lymph node with a diameter of the short axis of less than 1.0 cm must increase by $\geq 50\%$ and to a size of 1.5×1.5 cm or more than 1.5 cm in the long axis.
3. At least a 50% increase in the longest diameter of any single previously identified node more than 1 cm in its short axis.
4. If FDG-PET imaging has been obtained, PD should only be designated if the CT criteria for progression have been met and the lesions are PET positive for patients with PET-positive disease prior to therapy. FDG-PET is not mandatory for surveillance of progression.

Response	Definition	Nodal masses	Spleen, liver	Bone marrow
CR	Disappearance of all evidence of disease	(a) FDG-avid or PET positive prior to therapy; mass of any size permitted if PET negative (b) Variably FDG-avid or PET negative; regression to normal size on CT	Not palpable, nodules disappeared	Infiltrate cleared on repeat biopsy; if indeterminate by morphology, IHC should be negative
PR	Regression of measurable disease and no new sites	≥ 50% decrease in SPD of up to 6 largest dominant masses; no increase in size of other nodes (a) FDG-avid or PET positive prior to therapy; one or more PET positive at previously involved site (b) Variably FDG-avid or PET negative; regression on CT	≥ 50% decrease in SPD of nodules (for single nodule in greatest transverse diameter); no increase in size of liver or spleen	Irrelevant if positive prior to therapy; cell type should be specified
SD	Failure to attain CR/PR or PD	(a) FDG-avid or PET positive prior to therapy; PET positive at prior sites of disease and no new sites on CT or PET (b) Variably FDG-avid or PET negative; no change in size of previous lesions on CT		
RD or PD	Any new lesion or increase by ≥ 50% of previously involved sites from nadir	Appearance of a new lesion(s) > 1.5 cm in any axis, ≥ 50% increase in SPD of more than one node, or ≥ 50% increase in longest diameter of a previously identified node > 1 cm in short axis Lesions PET positive if FDG-avid lymphoma or PET positive prior to therapy	> 50% increase from nadir in the SPD of any previous lesions	New or recurrent involvement

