5 STUDY POPULATION

5.1 Inclusion Criteria

Each patient must meet all of the following inclusion criteria to be enrolled in the study:

1. Male or female patients 18 years or older
2. Patients with relapsed or refractory EBV- and CD30-positive lymphomas
 - a. EBV-positivity determined by EBV *in situ* hybridization at participating centers
 - i. Extranodal NK/T-cell lymphoma, nasal type
 - ii. EBV-positive peripheral T-cell lymphoma, not otherwise specified
 - iii. EBV-positive diffuse large B-cell lymphoma of the elderly
 - iv. Plasmablastic lymphoma
 - v. Lymphomatoid granulomatosis
 - vi. Hydroa vacciniforme-like T-cell lymphoma
 - vii. Other EBV-positive lymphoproliferative disorders
 - b. CD30-positivity determined by a specialized hemato-pathologist. CD30 positivity defined as 10% or greater tumor cells expressing CD30 at any intensity greater than or equal to 1+ with any cellular distribution pattern.
 - c. Relapsed or refractory disease that fails to at least one and maximum four regimens including anthracycline-based chemotherapy; if anthracycline-based regimen is not standard treatment of certain subtypes (e.g. hydroa vacciniforme-like T-cell lymphoma or EBV-positive lymphoproliferative disorder, etc), a prior chemotherapy is acceptable.
3. ECOG Performance status 0-2
4. At least one measurable lesion based on revised Cheson's or modified SWAT criteria
5. Provision archival tumor tissues (4 μ m thickness x 5 unstained slides) and blood samples
6. Adequate hematologic function: absolute neutrophil count (ANC) \geq 1,500/ μ L, platelet count \geq 75,000/ μ L, and hemoglobin \geq 8.0 g/dL unless there is known hematologic tumor marrow involvement (ANC \geq 1,000/ μ L and platelet count \geq 50,000/ μ L if there is known bone marrow involvement)
7. Adequate liver function: total bilirubin $<$ 1.5 x the upper limit of the normal (ULN) unless the elevation is known to be due to Gilbert syndrome and ALT or AST $<$ 3 x ULN (AST and AST $<$ 5 x ULN if their elevation can be reasonably ascribed to the presence of hematologic tumor in liver)
8. Adequate renal function: serum creatinine $<$ 2.0 mg/dL and/or creatinine clearance or calculated creatinine clearance $>$ 40 mL/minute.
9. Expected survival $>$ 3 months

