7.1.1 Determination of Sample Size

Optimal Simon's two-stage design

- $\alpha=0.05$, $\beta=0.20$
- $P_0=0.20$, $P_1=0.45$
- Stage 1: 2/10 (≥ 3 responders are required to move to stage 2)
- Stage 2: 7/22 (8 or more responses are required to reject the null hypothesis)
- Total patients: $22 + 3$ (10% drop-out rate) = 25 patients

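### Appendix 12.3: the partial-remission text gives no credit for shrinkage of a measurable lesion outside nodes, spleen, liver and skin, and conflicts with its own summary table, so the primary ORR can be scored in two ways

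*Combined protocol and SAP*

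**What the plan says.** Section 3.1 makes ORR the primary endpoint, scored by the revised lymphoma criteria (Appendix 12.3) or, for cutaneous lymphoma, by mSWAT (Appendix 12.4).

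The numbered partial-remission (PR) items in Appendix 12.3 treat lesions by site:

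- Item 1 requires at least a 50% "decrease in sum of the product of the diameters (SPD) of up to 6 of the largest dominant nodes or nodal masses".
- Item 3 requires at least 50% regression of splenic and hepatic nodules.
- Item 4 covers everything else: "With the exception of splenic and hepatic nodules, involvement of other organs is usually assessable and no measurable disease should be present".

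The summary table at the end of the appendix is worded differently. Its definition column describes PR as regression of measurable disease, with no limit to nodes. Its size rule speaks of dominant masses, but sits in a column headed for nodal masses. The only other site columns are for spleen and liver and for bone marrow.

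Section 5.1 accepts at least one measurable lesion, wherever it lies, and the first histology on its list is "Extranodal NK/T-cell lymphoma, nasal type".

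Section 7.1.1 sets a Simon two-stage design in which "3 responders are required to move to stage 2" out of 10, and "8 or more responses are required to reject the null hypothesis" out of 22.

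**The concern.** A patient can enter on a measurable lesion for which the PR text has no shrinkage rule. If that lesion lies outside nodes, spleen, liver and skin, and remains measurable, item 4 blocks PR however much it has shrunk. The first stable-disease item then takes in anyone who meets neither CR, PR nor progression. Growth is treated differently: the second progression item counts an increase in the size of other lesions.

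The decision rule turns on few patients (3 of 10, then 8 of 22), so one or two reclassified partial remissions can change the result. Sections 4.1 and 7.1.6 describe no central review of response that would impose one reading across centres.

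**Working it through.** **Step 1. Trace one lesion through the appendix.** Take a PET-positive nasal, lung or soft-tissue mass that shrinks by 70%, stays measurable and stays PET positive, with no new lesions.

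| Rule in Appendix 12.3 | Result |
|---|---|
| CR, item 4 (PET-negative residual mass allowed) | Not met: still PET positive |
| PR, item 1 (nodes or nodal masses) | Gives this lesion no credit |
| PR, item 3 (splenic and hepatic nodules) | Does not apply |
| PR, item 4 (other organs) | Fails: measurable disease remains |
| Progression items | Not met |
| SD, item 1 (not CR, PR or progression) | Met: stable disease |
| Table, PR definition column | PR if read on its own |
| Table, PR size rule | PR if *masses* is read broadly; not if the column heading governs |

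The text and the table can therefore classify the same patient differently, and nothing says which prevails.

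**Step 2. Reproduce the plan's design.** Inputs from Section 7.1.1: null ORR 0.20, target ORR 0.45, α 0.05, β 0.20, stop at 2 or fewer of 10, reject the null at 8 or more of 22.

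Power(p) = Σ over x = 3 to 10 of P(X₁ = x) × P(X₂ ≥ 8 − x), with X₁ ~ Bin(10, p) and X₂ ~ Bin(12, p).

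- p = 0.20: rejection probability 0.049, early stop 0.678, expected N 13.9.
- p = 0.45: power 0.806, early stop 0.100.
- Drop-out: 22 / 0.90 = 24.4, rounded up to 25.

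The stated design reproduces and is not in question.

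**Step 3. Illustrate the possible loss.** Let g be the share of patients whose PR would be blocked, and s the share of responses that are PR rather than CR. ORR is taken as CR plus PR, which the plan does not spell out. If every affected PR is lost and all CRs are kept:

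p_scored = 0.45 × (1 − g × s)

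The documents do not give g, so 10% to 50% is assumed. For s, the protocol's background gives:

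- DLBCL (Section 1.5): ORR 40%, CR 16%, so s = (40 − 16)/40 = 0.60 (CR share 40%).
- sALCL (Section 1.4): ORR 88%, CR 59%, so s = (88 − 59)/88 = 0.33 (CR share 67%).
- HL (Section 1.4): ORR 75%, CR 33%, so s = (75 − 33)/75 = 0.56, between the two.

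Example: g = 20%, s = 0.60 gives 0.45 × (1 − 0.12) = 0.396, and power 0.65.

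| g (assumed) | Scored ORR, s = 0.60 | Power | Scored ORR, s = 0.33 | Power | Chance of stopping at stage 1 |
|---|---|---|---|---|---|
| 0 | 0.450 | 0.81 | 0.450 | 0.81 | 0.10 |
| 10% | 0.423 | 0.73 | 0.435 | 0.77 | 0.12–0.13 |
| 20% | 0.396 | 0.65 | 0.420 | 0.73 | 0.14–0.17 |
| 30% | 0.369 | 0.55 | 0.405 | 0.68 | 0.16–0.22 |
| 50% | 0.315 | 0.35 | 0.376 | 0.58 | 0.21–0.34 |

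The calculation also assumes that affected patients respond as often as the others, with the same split between CR and PR.

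**The case against.** A reader might infer that the criteria measure only nodal disease, that patients with extranodal disease cannot be scored PR, and that the ORR is therefore biased down. The documents do not support that much:

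- Splenic and hepatic nodules are measured (item 3), and cutaneous lymphoma has its own PR under mSWAT.
- A patient whose other-organ disease clears can still be PR on nodal shrinkage.
- A residual mass of any size in a patient who was PET positive at baseline can be CR once it is PET negative. Lesions that stay PET positive, are not FDG-avid or are not scanned remain at risk. PET is mandatory only where a scanner is available (Schedule of Events, note i).
- The table's PR definition is not limited to nodes, and PR item 7 refers to any previously involved site. For variably avid or PET-negative disease, the table's stable-disease row expects no change in lesion size, which a 70% shrinkage does not fit.
- Item 4 is hedged: it says what is usual in other organs.

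These points stand. They show a conflict between text and table, not a rule that always forces stable disease, so downward bias follows only from literal use. They do not remove the gap, because no PR item states a percentage decrease for a measurable lesion at these other sites.

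The share g is also unknown; being first on the eligibility list says nothing about enrolment. It can further be said that the appendix only restates published criteria. That cannot be checked from the documents. In any case the appendix is already adapted to this trial, with EBV in situ hybridization added to the marrow items, and it has to work for the patients enrolled.

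**Conclusion.** Wrong as written. For measurable lesions outside nodes, spleen, liver and skin, the PR text and the summary table in Appendix 12.3 conflict on the primary endpoint. Under the text, a lesion that shrinks by at least half but stays measurable and is not PET negative is lost from the ORR. If some assessors follow the table, like patients are scored differently.

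Any bias is downward, so it threatens power rather than the type I error. Its size cannot be derived from the documents. The power range of 0.73–0.77 at g = 10% down to 0.35–0.58 at g = 50%, against 0.81 as planned, is an illustration. It rests on an assumed g, on response splits borrowed from other lymphomas, and on the worst case that every affected PR is lost.

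**What to change.** Before responses are assessed, amend Appendix 12.3 so that text and table agree:

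1. Item 1: include measurable extranodal lesions, with nodes and nodal masses, among the up to six target lesions in the sum of products.
2. Item 4: limit it to organ involvement that is assessable but not measurable.
3. Table: retitle the column *Nodal and measurable extranodal masses*.

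The cost is a change of appendix wording and a documented adaptation of the cited criteria. No extra scans or patients are needed, and the 2/10, 7/22 design stays as it is, with power 0.81 at a true ORR of 45%.
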